1. Age 65 years or older referred for physical therapy evaluation for symptoms of dizziness, postural instability, or both
2. Able to walk without the physical help of another person, with or with no assistive device
3. Able to follow commands and execute the examination and intervention instructions in the English language
4. Willing to participate in a phone interview four weeks after discharge
5. Able to provide informed consent

Exclusion Criteria

1. Unstable medical issues, such as unstable or uncontrolled cardiovascular conditions, elevated blood pressure (Systolic greater than or equal to 140mmHg and diastolic greater than or equal to 90mmHg), orthostatic hypotension (a fall in systolic blood pressure of at least 20mmHg or diastolic blood pressure of at least 10mmHg when a person stands from a sitting or lying down position), uncontrolled metabolic disease, as determined by the evaluating physical therapist, documented in the Functional Comorbidity Index, vital signs and assessment portion of the initial evaluation.
2. History of falls from syncopal origin
3. Dizziness of central origin, such as stroke, head injuries, MS or PD;
4. Active BPPV (patients with positive dix hallpike and/or roll test)
5. Inability to walk without physical assistance.

Resources Available

Each site will have research staff (treating physical therapists). Prior to enrollment of subjects, training of the study coordinator and research staff will be conducted onsite or online by the principal investigator. This training will cover the following: multi-site communication, subject recruitment, informed consent, inclusion and exclusion criteria and data collection. Research staff will receive instructions on randomization, interventions, outcome measures, and the use of Fitbit Zip pedometer. To establish interrater reliability, participating therapists will rate the DGI, mCTSIB and TUG by watching a video of a volunteer patient, and the DHI and IPAQ short form sample

questionnaires. To ensure compliance with the outcome measure equipment, research staff will sign a Research Equipment Compliance Document. The principal investigator will conduct inspection of equipment in each site, co-sign the document and keep the paper record in a locked filing cabinet in Florida Hospital.

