Visit 2: The research staff can initiate the research intervention according to the intervention group.

Visit 3 to visit prior to discharge: The research staff can continue the VR and intervention according to the intervention group.

Discharge or last visit: All outcome measures (DGI, TUG, mCTSIB, DHI and IPAQ) will be reassessed. Discharge scores for DGI, TUG, mCTSIB and DHI are standard of care, while IPAQ is for research purposes only. The total number of visits and length of

interventions (in weeks) for every participant will be recorded as secondary outcome measures. These research data will be forwarded to the study coordinator, and will be stored in a locked cabinet and password protected Florida Hospital computer.

Four-weeks after discharge: The study coordinator will conduct a follow up phone call to all subjects four weeks after discharge summary is completed to obtain the level of physical activity using the IPAQ short form questionnaire. This is for research purposes only. A follow-up on a subject will be discontinued if a subject is not reached after three attempts of follow-up phone call made on three different days between 30 and 45 days. Data analysis will commence once all the data from 54 subjects are collected.

Table 1. Summary of Interventions for VRWP, VRW and VR Groups.

VRWP (n=18)	VRW (n=18)	VR (n=18)

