Analyses will employ five repeated measures Analysis of Covariance (ANCOVA), adjusting for age, with two independent variables (group and time) and five outcome measures (TUG, DGI, DHI, mCTSIB and IPAQ short form). The adjustment of age is based on age-related decline. Intraclass Correlation Coefficient will be calculated to establish the test-retest reliability of the TUG and a stepwise linear regression with age as covariate will be conducted for all 54 subjects at baseline to determine if TUG, mCTSIB and DGI are predictors of DHI. Two-tailed test will be utilized to compare the compliance with step log recording and meeting step goals between the two walking groups (VRWP and VRW), and ANOVA to compare of total number of visits and total length of intervention in weeks between the three groups. Alpha for all analyses will be set at 0.05 to test for significant difference.

Potential Risks and Benefits

Potential Benefits

Possible benefits include improved physical function.

Potential Risks

The addition of a prescribed walking program in the treatment of dizziness will challenge the subject's balance, and in rare cases may result in falls or more dizziness.

Performance-based outcomes such as mCTSIB, DGI, and TUG check for the subject's reaction whenever in a condition of unsteadiness. The risks associated with these tests are the potential for falls and for dizziness. Self-report questionnaires such as the DHI and IPAQ will need the subject to read the questions and recall past experiences. Looking down and reading the questions may provoke dizziness and eye strain. Other possible risks for subjects are: 1) finding the questions to be sensitive 2) emotional discomfort (uncomfortable/embarrassed/sad/tired) and 3) distress as subject thinks of experiences.

Mitigation of Risks

The research staff (treating physical therapist) will supervise the treatment at all times to minimize any such risks.

Provisions to Protect the Privacy Interest of Subjects

Subjects will be assigned research numbers for study-related records and data sharing. The patient's confidentiality will be protected by observing the HIPAA policies and procedures.

Early Withdrawal of Subjects

Investigator Withdrawal of Subjects

The PI may terminate the participation of the subject in the study if the subject may be in any danger or no longer meets the inclusion criteria of the study.

Subject Request for Withdrawal from Study

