Subjects may withdraw or take away the permission to use and disclose their health information for any reasons at any time. This can be done by sending a written notice to the PI. Information that has already been gathered may still be used or given to others, however no new health information that might identify the subject will be gathered after the subject withdraw from the study.

Data Collection and Follow-up for Withdrawn Subjects

Patients who request withdrawal or who are withdrawn by the PI from the study will have their information that has already been gathered and shared in the research database. These data will be included in the data analysis. The percentage of patients withdrawing will be calculated.

Adverse Event Reporting

At each therapy visit of the subject, the research staff/treating therapist will seek information if there is any adverse event caused by taking part in the study. In the event of a research-related injury, the subject should report this in person or by phone to the research staff/treating therapist and PI. All adverse events will be reported to Florida Hospital's IRB and Nova Southeastern University's IRB following their respective policies for reporting adverse events.

Safety Monitoring Plan

Safety Monitoring
N/A

Data and Safety Monitoring Board (DSMB) or Equivalent
N/A

Ethical Considerations

Subjects in the VRW and VR group will receive a pedometer after they completed the study.

Sharing of Results with Subjects

Results of the study that are part of standard physical therapy will be shared with subjects and referring physicians. Letters will be sent to all participants that contain the results of the research once the research is completed.

Funding Source

Application for funding will be done through the Adventist University in January 2018. The principal investigator is currently requesting managers to allow the allocation of her Continuing Education budget for 2018 for this study.

Subject Stipends or Payments

The pedometer will be donated to the 54 participants, who met the inclusion and exclusion criteria and randomized into one of the three treatment groups, as a reward for participating in the research study and for them to perpetuate their physical activity.

Publication Plan

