All statistical analyses were performed using SPSS version 26. Mean and standard deviation were used to describe interval and ratio data, and frequencies for nominal data. Statistical significance was set at alpha <0.05. Since the parameters of a normal distribution were not met, nonparametric statistical tests were chosen for statistical analysis.

Objective 1. To evaluate the impact of walking as an exercise component of VR on both primary and secondary vestibular-specific outcome measures.

Mean and standard deviations on the mean differences of pretest and posttest of TUG, DGI, DHI, and mCTSIB were calculated to compare walking (VRWP + VRW) and control groups (VR only). P-value was calculated using the Kruskal-Wallis test to check for between-group differences in the primary and secondary outcomes. For within-group differences, the Wilcoxon Signed Rank Test was used to examine significant differences between the pretest and posttest.

Objective 2. To evaluate whether pedometers increase the adherence of older adults with vestibular issues to a walking program.

To compare the VRWP, VRW and VR groups, IPAQ-Walk and IPAQ-Total scores were categorized as improve, same or decline in pretest and posttest, posttest and four-weeks follow-up, and pretest and four-weeks follow-up. P-value was calculated using the Kruskal-Wallis test to check for between-group differences of sociodemographic data, IPAQ-Walk, IPAQ-Total, compliance in meeting step goals and compliance in step log. Friedman's 2-way ANOVA by ranks test was used to examine significant differences within the group.

Objective 3. To establish test-retest reliability of the TUG test on older adults with dizziness.

Intraclass Correlation Coefficient (ICC) was calculated using the two-way mixed model, consistency type on a single measure model with a 95% CI for relative reliability. For absolute reliability, the Standard Error of Measurement (SEM), Minimal Detectable Change (MDC) 95% CI, and Bland-Altman 95% level of agreement were examined. The SEM provides the range of scores on retesting. A smaller value of SEM means the calculated score is close to the true score.⁴⁴ The MDC is used to reflect the true change in score that exceeded the errors of measurements. Both the SEM and MDC are the same units of the original measures, which allows easier interpretation of results when applied in the clinical practice.⁷⁴

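### Withdrawal by the principal investigator can remove poor responders from the walking v VR comparison, and the plan neither secures their discharge scores nor asks for withdrawals by arm

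*Combined protocol and SAP*

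**What the plan says.** Under Investigator Withdrawal of Subjects, the PI may terminate participation "if the subject may be in any danger or no longer meets the inclusion criteria of the study". Inclusion criterion 2 is "Able to walk without the physical help of another person, with or with no assistive device". Resources Available states that the PI is also a treating therapist, and no blinding is described.

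Under Data Collection and Follow-up for Withdrawn Subjects, subjects who leave by either route "will have their information that has already been gathered and shared in the research database". The section continues: "These data will be included in the data analysis". Its only reporting instruction is "The percentage of patients withdrawing will be calculated".

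For Objective 1, the Data Analysis section states: "Mean and standard deviations on the mean differences of pretest and posttest of TUG, DGI, DHI, and mCTSIB were calculated", comparing the two walking arms together with VR alone. It adds: "P-value was calculated using the Kruskal-Wallis test to check for between-group differences in the primary and secondary outcomes". Neither the Statistical Analysis Plan nor the Data Analysis section says what happens when a posttest is missing.

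Study Visits has all outcomes reassessed at discharge or the last visit, and notes that "Discharge scores for DGI, TUG, mCTSIB and DHI are standard of care". Potential Risks says that prescribed walking challenges balance and may, rarely, lead to falls or more dizziness.

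**The concern.** Both withdrawal triggers are post-randomization events related to outcome. Needing another person's help to walk is close to what TUG and DGI measure, and these are two of the four primary outcomes. The danger trigger overlaps with a stated, though rare, risk of the walking programme, which only VRWP and VRW receive. The decision rests with someone who treats subjects and is not described as blinded.

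Keeping a withdrawn subject's existing data does not help Objective 1 if only the baseline exists, because a baseline alone gives no change score. If such losses fall more on the walking arms, the comparison is made among walkers who coped against all VR subjects, and the error favours walking. A single overall withdrawal percentage would not show this.

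**Working it through.** **The route to loss.**
1. A subject is randomized and has baseline TUG, DGI, mCTSIB and DHI.
2. The subject comes to need another person's help to walk, or is judged to be in danger, and the PI ends participation.
3. Data gathered so far are kept. If no final test was done, there is no posttest.
4. Change = posttest minus pretest is undefined, so the subject contributes nothing to the four primary comparisons. Baseline data still serve Objectives 3 and 4, and visits and weeks up to withdrawal could still be counted.

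**Inputs.** The plan gives 36 walkers (18 + 18), 18 VR subjects, a two-group Kruskal-Wallis test at 0.05, and 10% dropout for all causes and arms (0.10 x 54 = 5.4). It gives no withdrawal counts. Assumptions: k = 1, 2 or 4 losses, all among walkers; no true effect; normal change scores with SD 1.

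**Mean bias, approximate formulas.**
- Exactly the worst k lost: bias = phi(c)/(1 - q), with q = k/36, c the q-quantile and phi the normal density. This gives 0.066, 0.119 and 0.213 SD.
- k lost at random from the worst quarter, whose mean is -phi(-0.674)/0.25 = -1.27 SD: bias = 1.27k/(36 - k). This gives 1.27/35 = 0.036, 2.54/34 = 0.075 and 5.08/32 = 0.159 SD.

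**Simulation (20,000 trials per cell, 36 v 18), rounded over repeated runs.**

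| Walkers lost | Bias (SD) | All rejections | Rejections favouring walking |
|---|---|---|---|
| 0 | 0 | about 5% | about 2.5% |
| 1 | 0.04-0.06 | 5-6% | 3-4% |
| 2 | 0.07-0.11 | 6-7.5% | 4-6% |
| 4 | 0.16-0.21 | 9-12% | 8-11% |

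The lower end of each range is random loss from the worst quarter; the upper end is loss of exactly the worst. The Data Analysis section reports non-normal data. With lognormal scores (sigma 0.6) the upper ends of the bias are 0.09, 0.16 and 0.25 SD, and overall rejection rates are within 0.6 points of the normal case.

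**Equal-share loss (exactly the worst, normal).** Losing 2/36 and 1/18, or 4/36 and 2/18, gives a mean bias of about 0.01 SD. Overall false positives are still about 6% and 8%.

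**What one percentage shows.** Losses of 4/36 v 0/18, 3/36 v 1/18 and 2/36 v 2/18 all print as 4/54 = 7.4%, although they imply different biases.

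**The case against.** The rule is a discretionary safety clause, and the documents call the walking risk rare. Four one-sided losses of poor responders would take up most of a dropout allowance meant for every cause and every arm. Testing at the last visit would catch an orderly stop. The planned tables of TUG, DGI, mCTSIB and DHI by group at admission and discharge could expose unequal loss if group sizes were printed. Data collection also appears to be over, since the Data Analysis section is in the past tense and reports a result, so changing the rule may come too late. All of this stands and limits the size of the point. It does not supply a rule for a missing posttest, a requirement to test at PI withdrawal, or a promise of group sizes or reasons.

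Several stronger readings are tempting and not supported:
- A reader might infer that anyone who stops walking unaided must leave. Assistive devices are allowed, staff may recommend one in any arm, and the PI may withdraw a subject but need not.
- A reader might infer that the discharge score is always lost or may not be used. The bar on gathering new identifying health information stands under Subject Request for Withdrawal from Study. For PI withdrawal the loss is an inference from the reference to data already gathered.
- A reader might infer that a split by arm is excluded. The text does not ask for one and does not forbid one.
- A reader might express the bias as a share of the planned f = .25. That conversion depends on a repeated-measures test and a correlation that the plan does not state.

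**Conclusion.** The concern holds as an exposure. Following the stated rule can take poor responders out of the primary walking v VR comparison, in a direction that favours walking if the losses are one-sided. Under the assumptions above, one loss is negligible, two are small (about 0.07-0.11 SD) and four matter (about 0.16-0.21 SD, with 8-11% of null trials favouring walking against 2.5%). Whether any such loss occurred cannot be told from the documents, and a reader should not infer that the results are biased.

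The split by arm settles the mean bias only. With equal-share loss of the worst responders the mean bias almost vanishes, but overall false positives still reach about 8% at 4/36 and 2/18. A table by arm is therefore necessary but not sufficient, and keeping the discharge scores is the better remedy.

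**What to change.** 1. In Investigator Withdrawal of Subjects: when danger arises or the walking criterion is lost after randomization, stop the walking instruction or the exercise concerned, not participation. Unless the subject withdraws permission, keep the subject in the assigned arm and use the standard-of-care discharge scores. The plan already keeps a VRWP subject in the group after a lost pedometer. If data collection is over, use charted discharge scores where permission and the IRB allow.
2. Report withdrawals for VRWP, VRW and VR separately, split into subject request and PI decision, with denominators.
3. Optionally, add a sensitivity analysis giving PI-withdrawn subjects with no discharge score the worst rank, by the same rule in all arms. Label it conservative: with walkers drawn from the worst quarter, rejections favouring walking fall to about 0.9-2.1% against 2.5%.

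The cost is a few lines of wording, one short table and one extra analysis. The split by who decided has to be taken from withdrawal notices and PI records. Subjects who withdraw permission are still lost.

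### Data gathered before withdrawal are promised to the analysis, but the named longitudinal tests in standard form drop subjects with a missing time point, chiefly for IPAQ

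*Combined protocol and SAP*

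**What the plan says.** All references are to the combined protocol and SAP.

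- **Data Collection and Follow-up for Withdrawn Subjects.** Information gathered before withdrawal is kept: "These data will be included in the data analysis". The percentage withdrawing is to be calculated.
- **Subject Request for Withdrawal from Study.** After withdrawal, "no new health information that might identify the subject will be gathered after the subject withdraw from the study", so later scores will normally be missing.
- **Study Visits, four weeks after discharge.** "A follow-up on a subject will be discontinued if a subject is not reached after three attempts of follow-up phone call". IPAQ is the only measure taken at this point.
- **Statistical Analysis Plan.** "Analyses will employ five repeated measures Analysis of Covariance (ANCOVA), adjusting for age", with group and time as factors, for TUG, DGI, DHI, mCTSIB and IPAQ. Tables compare the first four at admission and discharge, and IPAQ at admission, discharge and four weeks.
- **Data Analysis, Objective 1.** Between groups, Kruskal-Wallis on pretest-posttest differences. Within groups, "the Wilcoxon Signed Rank Test was used to examine significant differences between the pretest and posttest".
- **Data Analysis, Objective 2.** IPAQ-Walk and IPAQ-Total "scores were categorized as improve, same or decline in pretest and posttest", and likewise for the other two pairs of time points, then compared by Kruskal-Wallis. Within groups, Friedman's "2-way ANOVA by ranks test was used to examine significant differences within the group".
- **Sample Size Determination.** The total of 54 includes 10% dropout.

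No analysis set, imputation, likelihood-based model or sensitivity analysis for missing scores is given anywhere.

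**The concern.** The withdrawal section says what will happen to partial data, and the methods named elsewhere cannot do it for the efficacy comparisons. A subject with only an admission score contributes to none of the pre-post or longitudinal tests. A subject with admission and discharge IPAQ but no four-week call loses both recorded scores from a standard three-time-point ANCOVA and from the Friedman test.

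This touches Objective 2 most, because the four-week IPAQ is part of the pedometer question. Loss related to arm and outcome is plausible: the protocol itself notes that dizziness restricts activity and that the walking programme may in rare cases cause falls or more dizziness. If people who walk less are harder to reach, and more so in one arm, a complete-case contrast can be shifted. The 10% dropout allowance covers numbers, not bias.

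**Working it through.** **1. What each method needs, in standard form**

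| Method | Outcome | Scores needed | Subject missing only the four-week call | Subject with admission score only |
|---|---|---|---|---|
| Repeated-measures ANCOVA | TUG, DGI, DHI, mCTSIB | admission, discharge | kept | dropped |
| Repeated-measures ANCOVA | IPAQ | all three | dropped | dropped |
| Wilcoxon (within group) | TUG, DGI, DHI, mCTSIB | both | kept | dropped |
| Friedman (within group) | IPAQ | all three | dropped | dropped |
| Kruskal-Wallis on differences | TUG, DGI, DHI, mCTSIB | both | kept | dropped |
| Kruskal-Wallis on change categories | IPAQ | both ends of each pair | kept for pretest-posttest, dropped for the two four-week pairs | dropped |

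An admission-only subject can still enter the baseline table, the TUG reliability analysis and the baseline DHI regression.

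**2. The plan's own figure.** The test, number of measurements and correlation behind 54 are not stated, so it cannot be confirmed from the stated inputs alone. One variant reaches it: a 3 × 3 group-by-time interaction with f = 0.25, alpha 0.05, power 0.80 and an assumed correlation of 0.3 needs 48, and 48/0.9 = 53.3, rounded up to 54. Under that variant, power is 0.86 with 54, 0.81 with 48 and 0.76 with 43.

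**3. Precision**
- Planned loss: 54 × 0.9 = 48.6.
- A further 10% loss (assumed): 48.6 × 0.9 = 43.7.
- Rise in standard error against the planned number: √(48.6/43.7) = √(1/0.9) = 1.054, about 5%.

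**4. What a mixed model recovers with two time points.** Take 10% of discharge scores missing at random, correlation ρ, equal variances, and age ignored. The standard error of the change, relative to full data, is:
- complete cases: √(1/0.9) = 1.054;
- all observed scores: √{[(1+ρ)/0.9 + (1−ρ)]/2}, which is √{(1.556 + 0.600)/2} = 1.038 at ρ = 0.4 and √{(1.944 + 0.250)/2} = 1.047 at ρ = 0.75.

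The gain is 1.054/1.038 = 1.015 down to 1.054/1.047, about 1.006: only 0.6% to 1.5% of the standard error.

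**5. Possible bias in the complete-case IPAQ contrast.** All inputs here are assumptions: 24% of one walking arm lost at four weeks, loss more likely with a low discharge score (logistic slope 1.0 to 1.5 per SD), 10% of control lost at random, and equal correlation ρ = 0.4 to 0.75 between time points. The gap in mean discharge score between kept and lost subjects is then about 0.85 SD (slope 1.0) or 1.11 SD (slope 1.5).
- Shift in the retained discharge mean = share lost × gap: 0.24 × 0.85 = 0.20 SD, or 0.24 × 1.11 = 0.27 SD.
- Regression to the mean leaves (1−ρ) of that shift in the discharge-to-follow-up contrast: from 0.25 × 0.20 = 0.05 SD to 0.60 × 0.27 = 0.16 SD, in the direction of a decline that did not occur.
- The complete-case admission-to-discharge contrast is off by the same amount with opposite sign. The admission-to-follow-up contrast is about unbiased, because both means shift by ρ times the same amount.
- Simulation with 18 per arm and slope 1.5 agrees: −0.165, −0.100 and −0.068 SD at ρ = 0.4, 0.6 and 0.75, against a truth of 0. An estimator using all observed scores was within 0.01 of the truth.
- The sampling standard error of this contrast is 0.40 at ρ = 0.4 and 0.26 at ρ = 0.75, so the bias is about 0.16/0.40 = 0.4 to 0.05/0.26 = 0.2 standard errors.
- If loss is unrelated to outcome, or equal in amount and pattern across arms, the between-arm bias is about zero.

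**The case against.** The strongest reply is that this is a reporting gap, not a contradiction. The withdrawal section says the data enter the analysis, not every longitudinal model, and baseline uses remain open. It speaks of withdrawn subjects, so it promises nothing about someone who simply cannot be reached. No section states complete-case deletion, and the ANCOVA sentence names no fitting procedure. All of that stands. What it does not answer is that the efficacy comparisons, in standard form, cannot use partial data, and no section says how they would.

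A reader might infer three stronger things that the documents do not support:
- *That the Wilcoxon and Friedman tests bias the arm comparison at follow-up.* Both are within-group tests, and Wilcoxon never uses the four-week score. The between-arm test in the Data Analysis section is Kruskal-Wallis, and its pretest-posttest comparison keeps subjects who miss only the call.
- *That missed calls affect the primary outcomes.* TUG, DGI, DHI and mCTSIB have no four-week score.
- *That precision falls by about 11%.* That figure, √(54/43.7), counts again the 10% dropout already built into 54.

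The bias calculation is also open to challenge. The unequal loss is assumed, and making loss depend on an observed score is the condition under which a likelihood model does well. Finally, the nonparametric tests were chosen because normality was not met, so discarding them for a normal-theory model would be a trade-off, not a correction.

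**Conclusion.** The point holds in limited form. The statement on withdrawn subjects' data can be met in the baseline table, TUG reliability and DHI regression, but not by the named efficacy tests in standard form. The practical loss falls mainly on IPAQ in the repeated-measures ANCOVA and the Friedman test.

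The size is modest. Losing a further 10% costs about 5% in standard error. Bias in the complete-case IPAQ contrast is possible but not shown: 0.05 to 0.16 SD rests on assumed unequal, outcome-related loss of 24% in one arm, and it vanishes under loss that is unrelated to outcome or alike across arms. It would be wrong to conclude that the trial's arm comparisons are biased, or that withdrawn subjects' data go wholly unused. The change is still worth making, because it is cheap and gives recorded scores a defined place in the analysis.

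**What to change.** - In the Statistical Analysis Plan, replace the repeated-measures ANCOVA with a linear mixed model (REML, unstructured covariance) per outcome, with arm, time, arm-by-time and age. Treat admission, discharge and, for IPAQ, four-week scores as responses, so that every observed score of every randomised subject contributes. Fit IPAQ-Walk and IPAQ-Total separately, transformed for skew.
- Report these models alongside the nonparametric tests in the Data Analysis section, not instead of them.
- State the analysis set, and say which analyses use data from withdrawn subjects.
- Report missing counts by arm and time point for each outcome, and add one sensitivity analysis for missing scores, for example assigning unfavourable values to those missing in the walking arms.

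The cost is SAP wording and a few extra model runs in the SPSS software already named. Because the Data Analysis section is written as completed work, this may have to be labelled a reanalysis. The model assumes missing at random, cannot recover an unmeasured discharge score, and gains little precision for the two-time-point outcomes.
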